4.1 Statistical Analysis

Summaries of each outcome (BADDs scores, performance on the cognitive tasks, Glut, and BOLD signal) under each treatment condition (baseline, LDX, and placebo) will be examined using histograms, boxplots, and normal probability plots. Transformations of the outcomes will be considered as necessary to meet modeling assumptions. General linear regression (mixed models) will be employed to estimate the association between each outcome, treatment condition and cross-over sequence while accounting for the nonzero correlation among the repeated observations within individuals.

Aim 1: Total BADDs score at each time point will be examined for an interaction effect between time (pre vs. post) and treatment (LDX vs. placebo) to assess whether within-subject total BADDs score is significantly reduced post LDX treatment rather than post placebo. Baseline BADDs scores will be dichotomized at the median score and considered as a covariate in the mixed effects models. Additional interaction terms for baseline group by time (pre vs. post) and baseline group by treatment (LDX vs. placebo) will be added to the model to test whether treatment effects differentially affect those with higher baseline scores.

Aim 2: Similar models will evaluate BADDs subscores, cognitive task performance, and L-DLPFC Glut levels. Similar mixed models will assess associations between change in specific BADDs domains with identified deficits in executive function and change in DLPFC Glut levels.

Aim 3: We will quantify associations between baseline percentage BOLD signal change during performance of the n-back (3-back) and L-DLPFC Glut.

Current methods for fMRI analyses are as follows: Functional scans will be realigned, normalized, time-corrected, and spatially smoothed by an 8 mm FWHW Gaussian kernel. The time series will be high-pass filtered to correct for drift across the scan. For blocked designed experiments (3-back), regressors will represent trial conditions; for the event-related design

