experiments regressions will represent individual trials and trial outcomes. At the individual level, voxel-wise fixed-effects contrast analyses will be performed for each subject to assess the magnitude of pair wise difference in blood oxygen dependent (BOLD) signal between the emotional and the neutral control condition. At the group-level, a second stage of the process will use a random effects model to create spatial parametric maps (SPM) depicting loci that are active across subjects. Movement parameters derived from the realignment correction (for all six possible directions) will be entered into the design matrix as covariates of no interest. For a priori regions of interests, clusters will be reported if they are significant at $P=0.05$ corrected, using a small volume correction (SVC). Clusters will also be reported if they are significant at a threshold of $P=0.001$, uncorrected, with an extend threshold of 10 voxels. Repeated measures analysis of variance (ANOVA) will then be performed to test the effect of LDX on brain activation patterns and simple effects analyses will reveal overall effects of LDX treatment.

fMRI/MRS Analysis: Percent BOLD signal changes in the left DLPFC will be entered in a correlational analysis with corresponding Glut concentrations. Size and orientation of regions included for analysis of BOLD signal and Glut concentration will be identical. Percent BOLD signal change will be calculated for each regressor of interest and correlation coefficients will be obtained. Voxel wise regression of BOLD signal vs. mean Glut concentration will be performed for each functional voxel.

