4.2 Rationale for sample size

Sample size is estimated for the 3 primary outcome measures: BADDS scores, DLPFC Glut levels, BOLD signal activation during the N-Back Task.

Assuming a type I, alpha, error of 5%, and 80% power, we anticipate being able to detect a 0.3 SD difference between within subject change under active LDX and placebo conditions with 88 participants. Based on our pilot data for total BADDS score, we will have 80% power to detect as small as an 8.4% difference in BADDS total score when comparing placebo to LDX administration. Given our pilot data from naturally menopausal women, this effect size corresponds to a 19% difference between active LSX and placebo in organization and activation for work, and 15% for attention/concentration BADDS subscales. We are conservatively powered for an effect size of 0.3 SD, meaning that we have sufficient power to examine a number of different covariates and possible predictors of outcome in this study.

Given our pilot data for levels of Glut in the left DLPFC, we will have 80% power to detect as small as a 2.6% reduction in Glut for active LDX administration compared to placebo. A similar 0.3 SD can be detected for BOLD signal in left DLPFC. This corresponds to a 25% difference in BOLD signal change between placebo and LDX for 3-back task.

5 Safety and Adverse Events

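### The second fMRI reporting rule calls clusters significant at uncorrected P=0.001 with 10 voxels, which leaves the map-wise false-positive rate uncontrolled and dependent on an unstated voxel size

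*Combined protocol and SAP*

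**What the plan says.** The fMRI part of section 4.1 has scans "spatially smoothed by an 8 mm FWHW Gaussian kernel". A group-level random effects model is then used to "create spatial parametric maps (SPM) depicting loci that are active across subjects".

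Two reporting rules follow:

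- **A priori regions of interest:** clusters are reported at P=0.05 "corrected, using a small volume correction (SVC").
- **Second route:** "Clusters will also be reported if they are significant at a threshold of" P=0.001, "uncorrected, with an extend threshold of 10 voxels". No region is named.

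The next sentence tests the effect of LDX on activation patterns by repeated measures ANOVA and gives no threshold. The fMRI/MRS paragraph adds a further mass-univariate analysis, also without a threshold: "Voxel wise regression of BOLD signal vs. mean Glut concentration will be performed for each functional voxel".

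The plan does not state voxel size, search volume, residual smoothness of the group maps or the direction of the tests, and it does not list the a priori regions.

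**The concern.** A per-voxel P of 0.001 applied over a large volume produces many chance exceedances. A minimum cluster size gives protection only if it is large relative to the smoothness of the map. Here the size is counted in voxels while the smoothing is in millimetres, so the error rate of the rule is undefined until voxel size is known. At common small voxel sizes, ten voxels occupy less than one smoothing element, and the extent requirement filters little.

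The plan nevertheless describes clusters passing this rule as significant, on the same footing as the corrected ones. At stake is the credibility of any localisation reported outside the a priori regions. The effect of LDX on executive system activation is a secondary outcome in section 1.3, so the question of which threshold governs the LDX maps also matters.

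**Working it through.** **The plan's own figure.** The plan states no error rate for the 10-voxel rule. The only design figure that can be reproduced is in section 4.2, which takes power of 80% and alpha of 5% and concludes: "we anticipate being able to detect a 0.3 SD difference between within subject change under active LDX and placebo conditions with 88 participants". With a two-sided normal approximation, ((1.960 + 0.842)/0.3)² = 87.2, rounded up to 88. It agrees, but it concerns the outcome measures (for BOLD, the left DLPFC signal) and says nothing about cluster error in maps.

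**Inputs.** From section 4.1: voxel threshold P=0.001 (z > u = 3.09), extent k = 10 voxels, 8 mm smoothing kernel. Assumed: search volume V = 1.3 litres, group-map smoothness F = 8 to 10 mm, voxel edge v = 2 to 4 mm, one contrast, one direction.

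**Extent against smoothing element.** At 8 mm the element is 8³ = 512 mm³. Ten voxels are 80 mm³ at 2 mm, 270 mm³ at 3 mm and 640 mm³ at 4 mm.

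**Random field formula.**

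1. Expected clusters above u: E = (V/F³)(4 ln 2)^1.5 (2π)^-2 (u² - 1) exp(-u²/2). With V = 1,300,000 mm³ and F = 8 mm, E = 21.4.
2. Mean cluster size in voxels: m = 0.001 × (V/v³)/E. At 3 mm: 48.1/21.4 = 2.25.
3. Chance that a cluster has at least k voxels: exp(-β k^(2/3)), with β = (Γ(2.5)/m)^(2/3). At 3 mm, β = (1.329/2.25)^(2/3) = 0.705, so the chance is exp(-0.705 × 4.64) = 0.038.
4. Expected false clusters: 21.4 × 0.038 = 0.81. Chance of at least one: 1 - exp(-0.81) = 0.56.

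At 2 mm the same steps give 5.0 expected clusters and a chance of 0.99. At 4 mm they give 0.064 and 0.06.

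**Simulation.** Null Gaussian fields in a 1.3 litre ellipsoid, z > 3.09, at least 10 connected voxels. The last column is the extent that would hold the map-wise rate at about 5%.

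| Voxel edge | P(at least one false cluster), smoothness 8 / 10 mm | Range over repeated runs | Extent for about 5%, 8 / 10 mm |
|---|---|---|---|
| 2 mm | 0.996 / 1.00 | 0.98-1.00 | 71 / 104 |
| 2.5 mm | 0.91 / 0.96 | single run | 38 / 66 |
| 3 mm | 0.56 / 0.78 | 0.51-0.78 | 21 / 35 |
| 3.5 mm | 0.19 / 0.48 | 0.19-0.48 | 15 / 23 |
| 4 mm | 0.035 / 0.21 | 0.03-0.21 | 10 / 16 |

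The formula tracks this closely; at 4 mm it is slightly higher (0.06 / 0.23).

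**Sensitivity.** If increases and decreases are both examined, over 1.2 to 1.5 litres and smoothness of 8 to 12 mm, the simulated range is 0.83 to 1.00 for 2 to 3 mm voxels and 0.07 to 0.67 for 4 mm. The formula gives 1 - exp(-2 × 0.81) = 0.80 at 3 mm, 8 mm and 1.3 litres. Several contrasts raise the chance of a false cluster further.

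**The case against.** The strongest objection concerns the drug question. A reader might infer that a null drug effect would usually still yield apparent LDX clusters. The documents do not support that. The two thresholds follow a description of group maps of active loci, and the LDX ANOVA is a separate step with no stated threshold. The rates above become LDX false-positive rates only if the ANOVA maps use the 10-voxel rule. On another reading, false activation clusters are picked independently of treatment and each is then tested for LDX at 0.05 (an assumed level). The simulated 0.7 to 5.9 false clusters per map (2 to 3 mm voxels) would then give at least one false LDX result with probability 1 - exp(-0.05 × 0.7) = 3% to 1 - exp(-0.05 × 5.9) = 26%. This objection stands, and the LDX consequence must stay conditional.

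A second tempting reading is that about half to all null maps contain a false cluster whatever the acquisition. That holds only for voxels of 3 mm or smaller. At 4 mm voxels and 8 mm smoothness the one-direction rate is about 3%, and ten voxels exceed the smoothing element. This also stands.

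Third, the plan does not say that the search is brain-wide. It is a reasonable inference from a rule with no region limit set beside one for a priori regions, but the 1.3 litre volume depends on it.

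Finally, the plan openly writes that the threshold is uncorrected, so an attentive reader is warned. That helps transparency. It does not give the rule an error rate, and the clusters are still called significant.

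**Conclusion.** The point holds in a conditional form. The second route has no multiplicity correction, no other section supplies one, and the map-wise false-positive rate is not controlled. Under one written rule, the chance of at least one false cluster runs from about 3% to about 100% as voxel size goes from 4 mm to 2 mm. These figures assume Gaussian fields, a brain-wide search of 1.3 litres, smoothness of 8 to 10 mm, one contrast and one direction. Within those assumptions, ten voxels is enough only near 4 mm voxels with smoothness no greater than 8 mm, a setting to which the plan does not commit.

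The reach is limited to findings outside the a priori regions. The primary outcome, total BADDs score (section 1.2), is untouched. So is the powered BOLD measure in section 4.2, a regional left DLPFC signal that does not depend on the 10-voxel route. Whether LDX maps and the BOLD-glutamate regression are exposed cannot be settled from the text; they are if they use this rule, and no other threshold is given for them. The sponsor should correct this before the maps are analysed, but it does not threaten the trial's main conclusion.

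**What to change.** Revise the thresholding sentences in section 4.1 as follows:

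- List the a priori regions and keep the small-volume-corrected 0.05 rule for them.
- Outside those regions, call a cluster significant only if it survives cluster-level family-wise correction at 0.05 over a stated search volume, with uncorrected 0.001 as the cluster-forming threshold.
- Apply the same rule explicitly to the LDX ANOVA maps and the voxel-wise BOLD-glutamate regression.
- State voxel size, how smoothness will be estimated, and whether one or both directions are tested.
- List clusters at uncorrected 0.001 with 10 voxels as descriptive only, with no inference about LDX.

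The change takes a few sentences and uses the same maps, with no new data. Its real cost is that fewer clusters outside the a priori regions will be reportable as significant.

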2.1 General Design

To further our understanding of the mechanism of LDX treatment in women with executive function complaints after risk-reducing bilateral salpingo-oophorectomy (RRSO), participants will undergo multi-modal imaging (fMRI and 1H-MTS at 7 Tesla) pre- and post- a 6-week course of LDX (20-60mg/d) or placebo followed by an approximate 2-week washout before crossing over to the other condition. This study utilizes a double-blind, placebo-controlled, cross-over design. We will recruit 100 women who are between the ages of 35 and 58 years old. Subjects will be recruited from flyers posted around campus, paid advertisements, referrals from collaborators at FORCE (Facing Our Risk of Cancer Empowered), the Basser Center, and other medical settings where women who have undergone RRSO may seek treatment. Study subjects will be screened by a member of the research staff who can gauge whether the individuals are likely to meet study criteria. Potential participants who appear to meet criteria and express an interest in the study will have the option of completing the screening visit remotely or completing the visit in-office. Participants will also have the option to complete a remote version of the study.

In-Office Screening: Participants who report for an in-office screening will be presented with the full, written ICF where they will have the chance to review and sign it with the study CRC. After giving full, written informed consent, subjects will undergo screening for past and current psychiatric disorders with the Mini International Neuropsychiatric Interview (M.I.N.I) and complete several behavioral ratings and questionnaires concerning personal history. A urine sample will be collected from participants to do a urine drug screen. Subjects will then undergo a brief medical evaluation and electrocardiogram (EKG) conducted by the study PI ([name], M.D.) or key study personnel. Vital signs including blood pressure and pulse will be recorded. Women with a consistent systolic blood pressure of >145mm Hg or diastolic blood pressure >90 mm Hg after three readings at screening will not be enrolled and referred to their primary care doctors for further evaluation. Routine laboratory studies will include TSH, FSH and estrogen assays. If potential subjects have had these tests performed within the previous 6 months and can present their results, they will forgo additional blood work except that for genetics studies (4 mL)

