End of Trial Scan: After the 6-week period, subjects will be scheduled to undergo their end of Trial A ¹H-MRS and fMRI scan session, which will take approximately 75 minutes. Subjects will be instructed to present to the Penn Center for Women's Behavioral Wellness approximately 2.5 hours before their scheduled scan to complete cognitive testing and behavioral assessments

regarding their mood and emotions. Subjects will then be escorted to the CMROI by the study CRC where they will be scanned and asked to perform a series of tasks assessing their memory and attention. In total, the end of Trial A scan will require approximately 4 hours to complete. The completion of this visit concludes all visits for Trial A. Upon completion of the visit and Trial A, subjects will be given the study drug for the entirety of Trial B (either placebo or LDX) and instructed to begin taking the medication after the washout period, as directed by the study provider.

Following an approximate 2-week washout period, subjects will complete their Trial B Baseline Visit, initiating the start of Trial B and medication usage. With the exception of the first baseline scan and cognitive testing, subjects will undergo the same study procedures for Trial B as they did for Trial A. Subsequent to their last scan, subjects will be required to bring their scales, blood pressure cuffs and unused capsules/empty bottles back to the study team so that they can be returned to Penn Investigational Drug Service (IDS).

The primary investigator and research staff will unblind themselves to the drug treatment that was administered in each trial upon each participant's completion or discharge from the study.

Remote End of Trial Visit: After the 6-week period, subjects will be scheduled to undergo their end of trial visit which will require approximately two hours. On the day of the remote end of trial visit, subjects will meet remotely with a member of the study team to complete behavioral assessments regarding their mood and emotions and complete cognitive testing. The completion of this visit concludes all visits for Trial A. Upon completion of the visit and Trial A, subjects will return the prescription bottle and any remaining study drug from Trial A so that they can be returned to Penn Investigational Drug Service (IDS). At this point, all subjects will be instructed to complete an approximate 2-week wash out period before continuing to Trial B.

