2.5 Compensation

Participants will be compensated for their participation in all study visits. If the participant completes all parts of the study, is on time for appointments, and takes her medication, total payment for participants is \$650.

The breakdown of subject payment by visit is as follows:

Visit Name	Visit Number	Amount
Screening Visit*	Visit 1	\$50
Trial A		
Baseline (with Scan)	Visit 2	\$150
Week 3*	Visit 3	\$50
End of Trial A (with Scan)	Visit 4	\$150
Trial B		
Baseline (without Scan)*	Visit 5	\$50
Week 3*	Visit 6	\$50
End of Trial B (with Scan)	Visit 7	\$150

Note: “” indicates that study visit can be complete remotely.*

Subject reimbursement is available for:

- Transportation to and from required in-office visits (Visits 2, 4, and 7).

- Hotel accommodations provided by the research team for up to two nights for required in-office visits (Visits 2, 4, and 7)
- Study-related procedures completed with the subject's physician that were NOT covered by the subject's insurance (i.e., EKG, blood work, and physical exam).

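### Section 4.1 points to two analyses for the LDX effect on BOLD, names a period term in neither, and does not say which one tests the LDX-versus-placebo hypothesis sized in 4.2

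*Combined protocol and SAP*

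**What the plan says.** Section 4.1 opens with a general rule: "General linear regression (mixed models) will be employed to estimate the association between each outcome, treatment condition and cross-over sequence". BOLD is among the outcomes it lists, and baseline is one of three treatment conditions: "Summaries of each outcome (BADDs scores, performance on the cognitive tasks, Glut, and BOLD signal) under each treatment condition (baseline, LDX, and placebo". The aim-by-aim text gives BOLD no treatment model of its own. Aim 2 extends the mixed models to BADDs subscores, cognitive tasks and Glut, and Aim 3 concerns only a baseline association between BOLD and Glut.

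The fMRI part of 4.1 describes first-level contrasts, group maps and cluster thresholds. It then states: "Repeated measures analysis of variance (ANOVA) will then be performed to test the effect of LDX on brain activation patterns", and adds that "simple effects analyses will reveal overall effects of LDX treatment". It names no factors, contrasts, period or sequence term, and no rule for missing scans.

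On the design, Section 2.1 says "This study utilizes a double-blind, placebo-controlled, cross-over design". The baseline scan is not repeated in the second period: "With the exception of the first baseline scan and cognitive testing, subjects will undergo the same study procedures for Trial B". The payment table in 2.5 agrees, listing Visit 5 as "Baseline (without Scan"; scans fall at Visits 2, 4 and 7 only.

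On status, 4.2 says "Sample size is estimated for the 3 primary outcome measures" and includes BOLD during the N-Back among them. Sections 1.2 and 1.3 make total BADDs the primary outcome and place BOLD under secondary outcomes.

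**The concern.** Two methods are named for the effect of treatment on one outcome, and they can give different answers. If the choice is left open until the data are in, the BOLD result depends on which sentence of 4.1 the analyst follows.

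Two features of the design make the details matter. First, baseline is always scan 1, while LDX and placebo are always scan 2 or scan 3. Randomising the order of LDX and placebo does not counterbalance baseline against either of them. If the unspecified simple effects include LDX against baseline, familiarity with the 3-back, scanner habituation and passage of time all enter the estimate as if they were drug effects.

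Second, the LDX-versus-placebo contrast is made across two periods. A change from the end of Trial A to the end of Trial B is noise in that contrast if it is not modelled, and bias if the scanned women are unevenly split between sequences. Uneven splitting among scanned women is possible, since 3.7 lets women take part without MRI and 3.1 expects 10% drop-out.

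**Working it through.** **Inputs.** From 4.2: alpha 5%, power 80%, effect 0.3 SD of the within-woman LDX-placebo difference, 88 women, with the same 0.3 SD quoted for BOLD. From 2.1 and 2.5: three scans per woman, baseline first. Assumed, because the documents do not give them: two-sided testing, the size of any order or period shift, and the sequence split. All shifts are in SD of the within-woman difference between two scans.

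**Step 1: the plan's own figure.** Paired comparison, normal approximation: n = ((1.960 + 0.842)/0.3)² = 87.2, rounded up to 88. This reproduces 4.2. With a paired t test, power at n = 88 is 79.5%. The calculation is for LDX versus placebo, not LDX versus baseline.

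**Step 2: what the baseline scan adds to that contrast.** Both treatments share one baseline scan, so (LDX − baseline) − (placebo − baseline) = LDX − placebo. Baseline cancels within each woman.

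**Step 3: LDX against baseline, no drug effect.** Let the later scans average m SD away from the first. The paired t test then has noncentrality m√88, and its rejection rate is the false-positive rate:

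| Assumed order shift m | False positives, n = 88 |
|---|---|
| 0 | 5% |
| 0.10 | 15% |
| 0.15 | 29% |
| 0.20 | 46% |
| 0.30 | 79.5% |

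**Step 4: LDX against placebo, sequences 1:1, period omitted.** Let the end of Trial B differ from the end of Trial A by s. The LDX-placebo difference has mean δ − s in women who take LDX first and δ + s in the others. The average is δ, so there is no bias, but the observed SD rises from 1 to √(1 + s²). There are two ways to turn that into power at δ = 0.3:

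- Treat the extra spread as ordinary noise, with effective effect 0.3/√(1 + s²). For s = 0.3 this is 0.287 and power is 76.0%. For s = 0.5 it is 0.268 and power is 70.2%.
- Hold the split at exactly 1:1, so that only the estimated standard error is inflated. Simulation gives 76.8% for s = 0.3 and 72.4% for s = 0.5. With a period term, power was 79.5% and 80.0% in the same runs.

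The two approaches differ because a fixed 1:1 split keeps the shift out of the sampling variance of the mean. Hence the ranges 76-77% and 70-72%.

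**Step 5: LDX against placebo, sequences 60:40 (LDX first : placebo first).** The mean difference is 0.6(δ − s) + 0.4(δ + s) = δ − 0.2s. With δ = 0.3 and s = 0.3 this is 0.30 − 0.06 = 0.24. In simulation, power was 57% without a period term and 78% with one, and type I error without the term was about 7%. The bias changes sign if the split or the shift is reversed.

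**Step 6: does the mixed model in 4.1 supply the missing term?** As written, it names sequence but not period. A sequence main effect compares women who took LDX first with women who took it second, averaged over both periods, and does not remove a change between periods. Steps 4 and 5 therefore apply to both analyses unless period is added.

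**The case against.** The strongest reply is that the ANOVA belongs to the voxel-wise mapping and the mixed model to a region-level BOLD summary, so there is no conflict. The ANOVA sentence does close a paragraph on parametric maps and speaks of activation patterns. This reading is possible, but the documents do not draw that line. The ANOVA comes after the maps are made, its stated purpose is to test LDX, and no sentence says which analysis addresses the BOLD difference sized in 4.2. That supports asking for one named test. It does not show that ANOVA is wrong in itself.

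A reader might infer several stronger criticisms that the text does not support:

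- That the ANOVA has no period term while the mixed model does. The ANOVA's factors are unnamed, so no term can be said to be excluded, and the mixed model does not name period either.
- That women with a missing scan will be dropped. That is how a conventional repeated measures ANOVA behaves, but the plan is silent on missing scans.
- That LDX will be tested against baseline. The simple effects are unspecified. Baseline appears as a condition in the sentence on descriptive summaries, and the only BOLD comparison quantified in 4.2 is placebo against LDX. The contrast is open, not planned.
- That a primary endpoint is at risk. BOLD is called primary in 4.2 only; 1.2 and 1.3 put it under secondary outcomes.

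It also stands that the period loss is modest with balanced sequences, and that every shift used above is assumed.

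**Conclusion.** The point holds as a gap in specification. Section 4.1 names two analyses for the LDX effect on BOLD, gives period in neither, and does not say which is the test.

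The larger risk is conditional. If LDX is compared with the always-first baseline scan, an order shift of 0.15 to 0.2 SD would produce about 29% to 46% false positives with 88 women. The smaller risk applies to the contrast that was sized: with balanced sequences, a power loss of about 3 points (shift 0.3 SD) to between 7 and 9 points (0.5 SD) and no bias; with a 60:40 split, bias of 0.2 times the shift.

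These figures assume two-sided 5% tests and 88 women with the scans needed. The documents give no practice or period effect and no number of women to be scanned. Because the repair uses data already being collected, it is worth making even if the true shifts are small.

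**What to change.** Name one test of LDX on BOLD in 4.1: left DLPFC percent signal change in the 3-back at the two end-of-trial scans, in a mixed model with treatment (LDX, placebo), period, sequence and a random effect for woman. Use all available end-of-trial scans and report LDX minus placebo with its confidence interval. Write period in explicitly; pointing to the existing mixed model is not enough.

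Label the ANOVA and the voxel-wise maps as supportive, and state that LDX against baseline will not be used as evidence of a drug effect. The baseline scan may enter as a covariate, though it adds little to a within-woman contrast. State the status of BOLD consistently in 1.3 and 4.2.

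The cost is SAP wording and one degree of freedom for period. No new data or visits are needed.
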